Many patients are members of the same family. As such, the research team will assemble family units (using household address, primary telephone number, patient ID of the guarantor, and insurance member ID as the variables of commonality to create these family units). For RCT 1, for each family, 1 individual will be randomly selected as the index patient. Only index patients who are also active portal users and affiliated with a primary care practice (criteria explained below) will have their data analyzed as part of the primary analysis plan. Secondary analyses will involve all study subjects.

Gender and age: We anticipate the gender distribution to be roughly equal. All ages of patients will be included in the study; however, patient will not receive a message until they are 6 months of age, as the flu vaccine is not recommended for those less than 6 months of age.

Racial and ethnic origin: There are no enrollment restrictions based on race/ethnicity.

Inclusion criteria

A patient at one of the clinics of interest within the UCLA Health System (up to 55 practices). An individual is deemed a primary care patient of the UCLA Health System through the following algorithm:

Assigned managed care patients (UCLAMG) + Attributed patients from other payers/ACOs

- ≥ 2 PCP visits in the past 3 years; or

- ≥1 PCP visit with preventive service code in past 1 year (99381-99397 or G0438/G0439)
- All visits cannot be urgent care visits (ie excludes visits after hours or on weekends, not by urgent care codes since UCLA does not bill accordingly)

Active patient: We decided to use the algorithm outlined above and currently approved and in place by the UCLA Health System as the research team believes it to be a generalizable model that could be applied to other health systems.

Exclusion criteria

Patients will be excluded from the overall study if they are not part of UCLA's primary care registry per the above algorithm detailed in the inclusion criteria.

Creating family units

An overall address field will be constructed from the data pull including the address, city, state, and zip code fields. Primary telephone number, patient ID of the guarantor and insurance member ID will be used as other variables in the process to create the family units. The following steps taken to create these family units is described below:

1. Start with a single entry in the contact data pull
2. Add any other entries with the same patient ID as any existing entry to the family

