Website link: the research team is working with UCLA marketing department to develop a new flu educational webpage. This webpage is currently under-development, but we will embed short health educational videos (examples below) on the UCLA website specific for this project:

<https://www.youtube.com/watch?v=EstDvA-mr5A>

<https://www.youtube.com/watch?v=QTjchoH1KYM>

The purpose of this website is to determine what subject areas of vaccine education (i.e. safety, effectiveness, general info) that patients are most interested in. All content will be approved by UCLA's marketing dept.

R/R Message Content: The content of each R/R message will be the same for each study arm. As discussed above we may modify the R/R message content slightly based the results of the prior RCTs and the qualitative interviews to follow. The number of R/R's sent will be based upon the optimal number from Aim 1 and will be identical for both study arms.

Please see item 1.0 for examples of the messages to be used (title: RCT #3 Reminders). Example message for Arm 2 same as that used in RCT #1.

Toolkit Development (Aim 3)

Toolkit and Adoption Guide: In the final year we will develop an online toolkit and adoption guide for portal-based R/R, with a manual of operations for algorithms, messages, data management protocols and costs for start-up and maintenance. Guides will contain FAQs and common scenarios, references, websites, and other materials for health systems to personalize portal R/R. We will use diffusion of innovation methods guided by our National Advisory Board. The toolkit and guide will be adaptable for pandemic flu vaccination R/R. Please note, should the language included in any of the messages outlines for RCT 1 - RCT 4 change, and amendment will be submitted.

MEASURES

After each RCT, qualitative provider and patient interviews will be conducted. Those procedures and measures are outlined in IRB submissions titled: Patient Portal - Patient Qualitative Interviews and Patient- Portal

Provider Qualitative Interview.

Independent Variables: The key variable is study group (portal R/R vs control).

Treatment Variables: Exposure to: (a) any portal R/R messages or (b) 1, 2 or 3 R/R's; see Analysis for RCT 1.

Covariates: Covariates considered for analyses (found in studies to affect flu vaccine rates) include: Practice variables will include type- (ex. pediatric, internal medicine, geriatric, or Med-Peds, and family medicine).

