Patient variables will include - age (6m-17y, 18-64y, 65+y), race/ethnicity, gender, primary language (by EHR), degree of portal use, and receipt of influenza vaccination in prior years. We recognize few UCLA patients have Medicaid; we will focus on low-income groups in the dissemination phase (Aim 3).

Dependent Measures

Vaccine Outcome: The primary outcome is influenza vaccination during the vaccination season as measured by analysis of EHR data. For children <9y who had not received prior influenza vaccination, the outcome will be at least 1 influenza vaccination.

Process Outcomes: These will include: (a) total # visits to the practice during the study time period, (b) # flu vaccine or nurse visits, and (c) missed opportunities. Visits will be measured by the EHR; using ICD-10/CPT codes to classify visits to primary care as preventive, acute/chronic, or nurse-vaccination. Missed opportunities are defined as # vaccine-eligible visits during which the patient did not receive an influenza vaccination. These process metrics will help assess how the intervention worked.

Additional Measures: see file: Summary of outcome measures RCT 1 which shows additional measures, grounded in the RE-AIM framework. Found in item 1.0 of this section.

Costs: Since the intervention is implemented centrally we assume no added practice costs. We also assume practice costs/vaccination from portal R/R is identical to standard practice costs/vaccination. We will assess the time and costs of study and implementation personnel and non-personnel costs, distinguishing planning costs from intervention costs. We will measure costs using a standardized time study/resource survey sent weekly to all individuals working on the study that delineates (a) the # hours spent for each individual, and (b) research vs implementation time. We will use national salary estimates by work code from the Bureau of Labor Statistics to value personnel time in standard rates. We will measure non-personnel costs EHR hardware, software, materials.

Cost and Cost Effectiveness

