Adjusting for clustering of patients in practices, and assuming an intraclass correlation (ICC) of 1% (consistent with previous work), this sample size provides >90% power to detect an overall difference of 5 percentage points between portal-based R/R (combining 1, 2, + 3 R/R arms) and 0 R/R arm for all users and subgroups of interest (age and race/ethnicity). The power for the subgroups corresponds to evaluating the treatment effect within each subgroup. These power analyses represent conservative estimates based on the available patient sample—we expect larger effect sizes based upon our prior R/R studies. An estimated number of index subjects is $1,248 \times 55 = 68,640$.

Statistical Analysis- Primary Outcome

Hyp. 2a.1: Patients receiving 1, 2, or 3 portal R/R will have higher influenza vaccination rates than 0 R/R.

Primary outcomes (patient receipt of flu vaccine) are binary; our main explanatory variable will be an indicator for the receipt of any portal-based R/R.

We will employ intent-to-treat analyses using mixed effects logistic regression models with practice random effects, an approach recommended for RCTs in which the goal is to estimate the causal effects of interventions on individuals, adjusted for patient correlation within practice. In addition to the treatment variable, the covariates in the model will include patient age (6m-17y, 18-64y, 65+y), race/ethnicity, gender, primary language, degree of portal use, flu vaccination in prior year, and practice type (internal medicine, family medicine, pediatric). This method performs well in situations where the number of observations per cluster is large and for unequal cluster sizes. Hypothesis tests will be two-sided and a p value < 0.05 will be considered statistically significant. We will use SAS v9.4 (SAS Institute Inc., Cary, NC).

Hyp 2a.2: More R/R messages will incrementally increase vaccine rates (3 R/R > 2 R/R > 1 R/R > 0 R/R): As above, we will use mixed effects logistic regression models.

The major difference for these analyses is that we will test for pairwise differences between consecutive study arms. With linear contrasts we can determine if each additional R/R increases vaccination rates. Bonferroni corrections will be applied to account for multiple comparisons. The expected sample size provides >90%

power to conservatively detect an OR of 1.13 between consecutive study arms (corresponding to a 3% increase in vaccination rates from the baseline rate of 42%).

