Statistical Analysis- Subgroup analysis

We will test Hyp. 2a.1 and 2a.2 stratifying by age (6m-17y, 18-64y, 65+y) and race/ethnicity (Hispanic, NH Black, NH Asian, NH White). We will apply Bonferroni corrections to account for multiple comparisons.

Statistical Analysis- Process measures

Because other process measures (# visits, # vaccination or nurse visits, and # missed opportunities) are count outcomes, we will use negative binomial mixed effects models to compare incidence rates between arms, controlling for the patient and practice covariates mentioned above.

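### Is the primary treatment variable what was sent to the patient, or the arm the patient was randomised to?

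*Combined protocol and SAP*

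**What the plan says.** Two places in the combined protocol and SAP describe the treatment variable in terms of delivery:

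- Statistical Analysis- Primary Outcome, under Hyp. 2a.1: "our main explanatory variable will be an indicator for the receipt of any portal-based R/R".
- MEASURES, Treatment Variables: "Exposure to: (a) any portal R/R messages or (b) 1, 2 or 3" reminders. This line then refers the reader to the analysis for RCT 1.

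Other places describe it in terms of assignment:

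- The sentence directly after the one on receipt: "We will employ intent-to-treat analyses using mixed effects logistic regression models with practice random effects".
- MEASURES, Independent Variables, one line above the exposure wording: "The key variable is study group (portal R/R vs control").
- Hyp. 2a.2: "we will test for pairwise differences between consecutive study arms".
- Process measures: "we will use negative binomial mixed effects models to compare incidence rates between arms".
- Power Analysis: the 5-point difference is between the combined 1, 2 and 3 reminder arms and the 0 reminder arm.

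**The concern.** Receipt is what happened to a patient; intent-to-treat concerns what the patient was allocated. The sentence that defines the primary regressor uses the first idea and the next sentence uses the second. If all assigned patients are sent a message, the two codings are identical. There are three ways in which they might differ:

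1. Infants. All ages are included, but a "patient will not receive a message until they are 6 months of age".
2. Registry patients who have not signed up for the portal, who cannot be messaged.
3. Patients vaccinated before the October send, if messages are then withheld from them. The paragraph on eligibility for reminders makes this conceivable.

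The third would do the most harm. The outcome definition sets no start date tied to the first message: "The primary outcome is influenza vaccination during the vaccination season as measured by analysis of EHR data". A patient in a reminder arm who was vaccinated in September and then skipped would be coded as untreated and vaccinated. That pushes the primary contrast downward, and few such patients would be needed.

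**Working it through.** **Inputs.** From Power Analysis: 42% vaccinated with no reminder; 45%, 47% and 49% in the three reminder arms, mean (45 + 47 + 49)/3 = 47%; 68,640 index patients. From the description of the 2018-19 RCT: 1:1:1:1 allocation within practices. This gives 68,640/4 = 17,160 controls and 51,480 patients in the reminder arms.

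**The plan's own figure.** For 42% against 47%, two-sided 5%:

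SE = √(0.42 × 0.58/17,160 + 0.47 × 0.53/51,480) = 0.00436, and 0.05/0.00436 = 11.5.

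Power is about 100%, in line with the stated figure of above 90%. Dividing the sample sizes by 1 - ICC = 0.99, for randomisation within practice, changes nothing visible. This calculation already uses assigned arms.

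**What literal receipt coding could do.** Assume that a share *f* of reminder-arm patients is vaccinated before the first send and that messages are withheld from some or all of them. Neither *f* nor a withholding rule is in the documents. Let *g* = *f* × share withheld. Then:

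- rate coded untreated = (0.25 × 0.42 + 0.75*g*)/(0.25 + 0.75*g*)
- rate coded treated = (0.47 - *g*)/(1 - *g*)

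| *f* | Patients recoded, all withheld | Difference, all withheld | Difference, half withheld | Difference, none withheld |
|---|---|---|---|---|
| 1% | 515 | +2.8 | +3.9 | +5.0 |
| 2% | 1,030 | +0.6 | +2.8 | +5.0 |
| 3% | 1,544 | -1.4 | +1.7 | +5.0 |
| 5% | 2,574 | -5.4 | -0.4 | +5.0 |

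Setting the two rates equal gives 0.5425*g* = 0.0125, so *g* = 2.30%, or about 1,186 of 51,480 patients. These are crude figures. The planned model adjusts for prior-year vaccination and portal use, which would alter their size.

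**What intent-to-treat coding does.** With the plan's rates taken as rates by assigned arm, the difference is +5.0 points whatever *f* is. Suppose instead that some reminder-arm patients were not reached and had the control rate. The difference would be 5.0 × 0.90 = 4.5 points at 10% unreached and 5.0 × 0.80 = 4.0 points at 20%, with power still about 100%.

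**Which coding the plan means.** The passages side by side:

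- Intent-to-treat has a settled meaning: a patient assigned to reminders but sent none stays in the assigned arm. That is the rule for the undelivered case.
- Hyp. 2a.2 is introduced as the same model, differing mainly in that consecutive arms are compared. So Hyp. 2a.1 is that model with arms pooled.
- OVERALL STUDY DESIGN says that patients are randomised to receive 0, 1, 2 or 3 messages, so the verb names the assigned regimen.
- Power Analysis describes the control rate as the rate without receipt and sets it beside the rates in the reminder arms. There *receipt* can only stand for arm.

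**The three routes.**

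1. Infants under 6 months are not in the computation above. They fall outside the model's age categories, which begin at 6 months, and vaccination is not recommended for them, so they do not fit the untreated-and-vaccinated pattern.
2. Lack of sign-up does not touch the primary analysis, which is limited to active portal users. In the full registry, the share of a no-receipt group that came from reminder arms would be 0.75(1 - *s*)/(0.25 + 0.75(1 - *s*)) at sign-up *s*: 0% at 100%, 37.5% at 80% and 55.2% at 59%. The last is an upper limit, since 59% is active use. No section specifies a receipt variable for that analysis.
3. Withholding after vaccination is not stated. The eligibility sentence is about whether a patient needs one or two vaccinations.

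**The case for a change.** The strongest case for a change is that the only sentence defining the primary regressor says receipt. The statement of Hyp. 2a.1 in the analysis section is also worded by what patients receive, and no section equates receipt with assignment. The documents allow the two to differ, the primary result would be fragile if they did (about 2.3% of reminder-arm patients would erase it), and the repair is a few words that cost nothing.

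Much of this stands. The wording is loose in two sections, the arithmetic is right under its assumptions, and writing *randomised to* would be tidier. What does not stand is the step from loose wording to a flawed analysis. An analyst would have to apply the receipt sentence literally and disregard the intent-to-treat sentence that follows it. The fragility then needs two further inputs that the documents do not supply. That the repair is cheap does not mean it gains anything: it would write down the contrast the plan already powers and already calls intent-to-treat.

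**Conclusion.** No change to the plan is needed. This is imprecise wording, not a contradiction left open. Read as a whole, the plan compares patients randomised to 1, 2 or 3 reminders with those randomised to none, and a patient sent no message stays in the assigned arm. On the plan's assumed rates that contrast is +5.0 points, with power near 100%, and neither figure would move if the text were reworded. The smaller or reversed differences (+2.8 to -5.4 points with full withholding and 1% to 5% vaccinated early) need three things together: intent-to-treat set aside, a withholding rule that the plan does not contain, and an assumed early-vaccination share. The conclusion rests on intent-to-treat carrying its ordinary meaning. Nothing in the documents suggests that it does not.

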Costs: We will assume that the actual per-dose vaccination costs (administration costs, vaccine costs, storage, etc.) are identical for intervention and comparison patients and equal to the average national reimbursement for an influenza vaccine dose. The difference in total costs between the study arms will be influenced by the total costs of implementing the intervention, the difference in vaccination rates within study arms, and the subsequent health care utilization by the population (which we can model from prior studies)

Effectiveness: For each RCT we will estimate effectiveness using model-based, standardized expected values (mean) at the end of each RCT. We will calculate incremental cost-effectiveness ratios (ICERs) for each intervention arm.

For example, to compare costs in RCT #1 for Arm 3 R/R's vs Arm 2 R/R's, the ICER is: $ICER (\text{Arms 3 R/R vs 2 R/R}) = (\text{costArm 3 R/R} - \text{costArm 2 R/R}) / (\text{Flu vaccine rateArm 3 R/R} - \text{Flu vaccine rateArm 2 R/R})$

In the numerator of the above equation, the costArm X is equal to [(# Flu vaccine doses given per study arm x average national vaccine reimbursement per dose) + average costs per patient in that Arm]. The denominator of the equation is the difference in model-based, standardized expected values at the end of the intervention.

STATISTICS AND ANALYTIC PLAN

Analytic Plan:

The primary outcome is receipt of influenza vaccine among eligible index patients comparing the effectiveness of 1, 2, or 3 MyChart flu reminders to zero MyChart flu reminders.

Secondary measures are receipt of influenza vaccine among all identified patients in the primary care registry (per the algorithm outlined above in the inclusion criteria), process metrics, # subsequent preventive visits, and costs.

Power Analysis:

Power was evaluated using a simulation study. We assumed a within-practice randomization plan, and expect at minimum the sample sizes reported in Table 3 (n=145,684). We further assumed, based on preliminary UCLA Health data, that influenza vaccination rates are 42% among portal users without receipt of any portal-based R/R, and 45%, 47% and 49% among users in the 1, 2, and 3 R/R arms. We estimate 1,248 portal user families per practice (we will select 1 subject per family), based on our estimated mean family size of 2.38 portal users per family, and up to 55 practices.

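### The outcome model adjusts for one prior year of flu vaccination where the covariate list names several; adding earlier seasons is a minor, cheap gain in power for the 2-point contrasts and subgroups

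*Combined protocol and SAP*

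**What the plan says.** The Covariates paragraph under Measures introduces a list of variables considered for the analyses. Among the patient variables it names "degree of portal use, and receipt of influenza vaccination in prior years". It gives neither the number of years nor the coding.

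The section Statistical Analysis- Primary Outcome sets out the mixed effects logistic model for Hyp. 2a.1. Its covariates end with "flu vaccination in prior year, and practice type (internal medicine, family medicine, pediatric" as the practice types, so vaccination history enters as one year. Hyp. 2a.2, which compares consecutive arms, refers back to the same type of model and names no other covariates. On testing, the section says "Hypothesis tests will be two-sided and a p value < 0.05 will be considered statistically significant"; for the consecutive-arm contrasts, "Bonferroni corrections will be applied to account for multiple comparisons", without giving the number of comparisons.

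For the control arm, the Power Analysis assumes that "influenza vaccination rates are 42% among portal users without receipt of any portal-based R/R". With one, two and three reminders the assumed rates are 45%, 47% and 49%. The planned steps are therefore 3, 2 and 2 points. Power is stated for a 5-point pooled difference and for a 3-point step. No figure is given for a 2-point step, and no allowance is made for covariate adjustment.

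**The concern.** Past vaccination is plausibly among the strongest baseline predictors of vaccination this season. If people differ persistently in their habit, one yes/no from last year measures that habit with error, and two or three seasons measure it better. Using fewer seasons than the covariate list suggests would then give up some power.

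The contrasts with least margin are 2 vs 1 and 3 vs 2 reminders, and the same contrasts within the age and race/ethnicity strata. The difference in wording also leaves the look-back open, since the plan does not say how many seasons count or how a patient without history is coded. That choice should not be made after the results are known.

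**Working it through.** **Inputs from the documents.** 1,248 × 55 = 68,640 index subjects; allocation 1:1:1:1, so 68,640 / 4 = 17,160 per arm; rates 42/45/47/49%; two-sided 0.05.

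**Assumptions.** Bonferroni over three consecutive contrasts, alpha 0.05/3 = 0.0167, critical value 2.394. Year-to-year correlation rho of 0.3 to 0.6, equal between any two seasons. Complete history.

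**The plan's own figure.** Power = Φ{ [Δ√n − z·√(2p̄(1−p̄))] / √(p1(1−p1) + p2(1−p2)) }, with √17,160 = 131.0.
- 42 vs 45% (OR 1.13): (3.930 − 2.394 × 0.7011) / 0.7008 = 3.21, power 99.9%. The stated >90% holds as a lower bound.
- 45 vs 47% (OR 1.084): (2.620 − 2.394 × 0.7048) / 0.7047 = 1.32, power 90.7%.
- 47 vs 49% (OR 1.083): 90.6%.
- Pooled: the reminder arms average (45 + 47 + 49)/3 = 47%, so z = 0.05 / √(0.42·0.58/17,160 + 0.47·0.53/51,480) = 11.5, power about 100%.

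The ICC of 1% hardly matters because randomisation is within practice: with n/(1 − 0.01) the 2-point steps have 91.0% and 90.9%.

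**Effect of k prior seasons.** Under equal correlation, R² = k·rho² / (1 + (k−1)·rho), and the effective n is n/(1 − R²). The gain of three seasons over one is (1 − R²₁)/(1 − R²₃) − 1. Power is for 45 vs 47% at alpha 0.0167.

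| rho | R², 1 season | R², 3 seasons | Effective n gain | Full sample, 1 → 3 seasons | One-third subgroup, 1 → 3 seasons |
|---|---|---|---|---|---|
| 0.3 | 0.090 | 0.169 | 9% | 93.4 → 95.4% | 44 → 48% |
| 0.4 | 0.160 | 0.267 | 15% | 95.2 → 97.4% | 48 → 54% |
| 0.5 | 0.250 | 0.375 | 20% | 97.1 → 99.0% | 53 → 63% |
| 0.6 | 0.360 | 0.491 | 26% | 98.8 → 99.8% | 61 → 73% |

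The 47 vs 49% step is within 0.3 points of these figures. The one-third share is an assumption, because stratum sizes are not given; any further subgroup correction would lower that column.

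**Check by simulation.** Random-intercept logistic persistence, 45 vs 47%, 17,160 per arm, 300 trials per setting. Mean z with one and with three seasons was 3.847 and 4.008 (correlation 0.29), 4.149 and 4.564 (0.47), and 4.703 and 5.261 (0.59). The squared ratios minus 1 give gains of 8.5%, 21% and 25%, in line with the table.

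**Where the gain shows.** In a simulation of this kind (correlation about 0.43), the standard error of the log odds ratio was 0.0240, 0.0251 and 0.0259 with one, two and three seasons. It rises. The conditional log odds ratio rises faster, and that lifts the test statistic.

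**Less favourable patterns.** With correlations of 0.5, 0.4 and 0.35 at one, two and three years, R² goes from 0.250 to 0.291, and the gain is 0.750/0.709 − 1 = 6%. A simulation with decaying correlation gave about 3%. If only the last year carries information, the gain is essentially nil (zero in the formula, about 1% in simulation).

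**Smaller sample.** The Power Analysis also says "expect at minimum the sample sizes reported in Table 3 (n=145,684"; divided by 2.38 portal users per family, that is about 61,212 index subjects. The 2-point steps then have 86.6-86.8% unadjusted, 89.9-97.7% with one season and 92.6-99.4% with three.

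**The case against.** The strongest reply is that nothing is wrong. The Measures list is one of candidates, and the analysis section makes a choice from it, which is normal practice. The 2-point steps have about 90.6% power with no covariates and about 93-99% as planned, so there is no shortfall to repair. The size of any gain rests on a correlation that the documents do not give, and the favourable cases assume every past season is equally informative. Infants and patients who qualify on a single preventive visit in the past year may lack older seasons. Subgroup contrasts of 2 points stay underpowered after the change. All of this stands, and it is why the point is minor.

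Three stronger readings are tempting, and the documents do not support them:
- **That the primary result is biased or at risk.** Arm is randomised, the covariate is measured at baseline, and the pooled test has about 100% power.
- **That one season gives wider confidence intervals.** For the planned log odds ratio the standard error rises as seasons are added. Intervals for the standardised rates used in the cost-effectiveness section could narrow, but that is a different quantity.
- **That the extra data are already in hand.** The eligibility rule looks back three years for visits, and the EHR must already check children under 9 for prior flu vaccination, so older records are probably obtainable. No section says how many seasons are extracted or how complete they are.

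A reader might also want age entered more finely than in three bands. No benefit from that has been worked out, and it is not part of this point.

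What the reply does not remove is that the look-back and the handling of missing history are unspecified, and that a better-specified covariate costs almost nothing.

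**Conclusion.** The point holds as a minor improvement in efficiency, together with a wording difference to settle. Under persistent habits, three seasons instead of one give about 8 to 25% more effective sample size. For the full-sample 2-point contrasts that means about 1 to 2 points of power; in an assumed one-third subgroup it means about 4 to 12 points. Where older seasons add little, the gain is about 3% or less. The pooled primary contrast and the 3-point step gain nothing that matters.

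The difference in wording between the two sections and the direction of the effect are well supported. The size depends on the assumed correlation of 0.3 to 0.6, on how it decays, on how complete the history is, and on three Bonferroni comparisons.

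**What to change.** In Statistical Analysis- Primary Outcome, replace the single prior-year term with separate indicators for each of the last three seasons available in the EHR. Give each season an added level for no usable history (no record, or not yet a patient), kept distinct from a season known to be unvaccinated. State that Hyp. 2a.2 and the subgroup analyses use the same terms, bring the Covariates paragraph under Measures into line, and fix all of this before the outcome data are analysed by arm.

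The cost is a longer look-back in the EHR extract and a few extra parameters among about 68,640 patients. The conditional odds ratio from the fuller model will not be numerically comparable with the unadjusted 1.13 in the power text, so the standardised rates should be reported beside it.
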